# 9.4 Statistical Analyses

# 9.4.1 General Approach

With the ITT Analysis Population, we will calculate baseline descriptive statistics by study arm using means and standard deviations for continuous variables, and frequencies and percentages for categorical variables. We will test for differences in potential confounders between intervention and control arms using baseline staffand school-level data with Rao-Scott chi-square tests for categorical variables and linear mixed models (with a random effect for school) for continuous variables (models adjusting for the clustering of staff within schools). Secondary analyses will adjust for imbalances between arms. For previously validated scales, we will report

internal consistency via Cronbach's alpha for continuous scales. For newly created items, we will conduct exploratory factor analyses to examine the dimensions of our outcomes as well as internal consistency using baseline surveys. We will use the most recent version of Stata. All tests are two-tailed and  $\alpha$ =0.05. Given the small sample size and pilot nature of these analyses, we will not perform any corrections for multiple tests.

Regarding qualitative analyses, we will transcribe, de-identify, and quality check all data. We will perform qualitative analyses in Dedoose. We will use CFIR as a guiding framework. Two qualitative coders will independently read interviews and compare coding until they agree they are on the same page. Once the coders, we will create a final codebook with definitions, rules, and examples for each code. Two coders will then recode all data using the final codes. We will calculate inter-rater reliability (i.e., Kappa statistic) to examine code application between coders. Coders will discuss any discrepancies until they reach agreement; [name] will resolve disagreements. We will use either a qualitative descriptive coding approach (wherein we describe and count the number of code applications) or axial coding (wherein we combine inductive codes into broader categories to define emerging patterns or themes). We will identify and interpret patterns in the data using a thematic analytic approach.

#### 9.4.2 Analysis of the Primary Endpoints

To answer our primary research question, we use best practices for pilot/feasibility studies. Thus, we will analyze our primary outcomes using descriptive statistics. We will not correct for multiple tests. AIM, IAM, and FIM are calculated as an average of their 4 respective items in the follow-up survey. We will calculate SUS as recommended. Among people in the PLANTS primary endpoint population, we will calculate means and 95% CIs for participants' responses to the FIM, AIM, IAM, and SUS. Our benchmarks of success are means > 3.75 out of 5 for AIM, IAM, FIM and scores > 75 out of 100 for SUS.

#### 9.4.3 Analysis of the Secondary Endpoints

#### Hypothesis: School staff will have high participation rates in the study (≥50% consent).

The Participation Rate equals the number of school staff who consent to participate divided by the total number of school staff who are invited. We will calculate an overall participation rate with a 95% confidence interval.

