# 5 STUDY POPULATION

# 5.1 Inclusion Criteria

# School Inclusion Criteria:

To be eligible to participate in this study, schools must meet all of the following criteria:

- Participated in the 2021 MetroWest Adolescent Health Survey (MWAHS)
- Plan to participate in the 2023 MWAHS
- Grant us permission to access their MWAHS data
- Willing and able to provide emails addresses for all school staff
- Willing and able to provide us a letter of support denoting their participation in our study

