#### 5.5 Strategies for Recruitment and Retention

#### School Staff

**Recruitment.** For high schools to be eligible to enroll in our study, school administrators must be willing to provide email addresses for all school staff members so that we can adequately recruit all staff in the high school. At the enrolled high schools, we will administer online surveys via REDCap to all staff members that interact with students (e.g., a census of teachers, administrators, nurses, counselors). We will email participants a screener survey to confirm their eligibility for participation, a consent form, and a baseline survey. We will also place study advertisements in their school mailboxes.

**Retention.** The follow-up survey will be delivered post-intervention. Several methods used by [name] and his mentorship team have proven valuable in retention of participants in longitudinal studies. To keep participants engaged, we will: inform participants at the beginning about the anticipated time burden and associated incentives; provide participants with clear instructions about their tasks; send personalized reminder emails and text messages to participants who have not completed a survey; email participants 1 day in advance of their survey, reminding them to look out for the upcoming survey email and to check spam filters; encourage participants to reach out to us when they have questions or concerns via email, phone, or text; and provide participants with escalating incentives that increase each survey. We will monitor retention on a weekly basis and more frequently if needed to ensure we are maintaining high retention.

**Incentives.** To incentivize school staff to complete the baseline survey, we will provide \$20 gift cards to each participant and will raffle \$30 gift cards to 20% of participants who take the baseline survey within each school. To incentivize school staff to complete the follow-up survey, we will provide \$30 gift cards to each participant who completes the survey will and raffle \$40 gift cards to 20% of participants who take the follow-up survey within each school. For staff who complete the follow-up interview, we will provide \$50 incentive as a thank you for their time.

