# Staff Screener (Time 0)

- 1. Inclusion/exclusion will be self-administered via REDCap by high school staff. These are the exact questions:
  - a. Which schools do you currently work at? [drop down list of MetroWest Schools + "Somewhere else" + write-in]
  - b. How often do you interact with students at your job? [0: Daily; 1: Weekly; 2: Monthly; 3: Yearly; 4: Never]
  - c. How old are you? [integer validation]
- 2. Informed consent: We will provide informed consent materials online via REDCap.

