#### Secondary Endpoint Hypotheses:

Regarding trial implementation and PLANTS safety, we hypothesize: school staff will have high participation rates in the study ( $\geq$ 50% consent); school staff will have a low attrition rate for the follow-up survey ( $\leq$ 25% drop-out); high school staff in the PLANTS arm will have high intervention demand ( $\geq$ 75% adhere to the intervention protocol); and high school staff in the PLANTS arm will have low adverse event prevalence ( $\leq$ 20% of PLANTS participants will report adverse events).

We hypothesize that participants in PLANTS will report greater active-empathic listening, greater self-efficacy for supporting, affirming, and protecting SGMY, and greater positive bystander intervention behaviors for bullying in follow-up surveys than participants in the active control arm.

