#### 9.2 Sample Size Determination

#### Primary Endpoints

To adequately evaluate the primary endpoints, we need precise estimates of acceptability, appropriateness, and feasibility. We calculated our sample size based on our primary outcomes, a 5% error rate, and best practices for feasibility studies. The median number of teachers at each MetroWest Region high school is n=86. With 4 schools in our sample, we anticipate inviting a total  $\geq$ 344 school staff to participate in the pilot study. Assuming 50% agree to participate, 50% of participants are in the PLANTS study arm, and 75% of PLANTS participants complete the follow-up survey (reduced n=65), we can estimate 95% CI widths  $\leq$ 0.33 for AIM, IAM, and (based on the largest upper CI limit of the AIM, IAM, and FIM standard deviations) and  $\leq$ 10.1 for SUS. Such precision levels are sufficient.

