# Secondary Endpoints

We anticipate inviting at least 344 school staff to participate in the pilot study, and assuming 5% type I error rate, we will be able to estimate a 95% confidence interval width of no more than 0.11 for the participation rate. Assuming a participation rate of 50% (n=172), we will be able to estimate a 95% confidence interval width of no more than 0.15 for the attrition rate. Assuming half of the consenting participants are in the intervention arm (n=86), we will be able to estimate 95% confidence interval widths of no more than 0.21 for the proportion of school staff who adhere to the PLANTS intervention and for the proportion of school staff who report adverse events.

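### The participation rate keeps staff who fail screening in its denominator, so confirmed ineligibility counts as non-consent against the 50% benchmark

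*Combined protocol and SAP*

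**What the plan says.** **Definition and benchmark.** Section 9.4.3 gives the rule: "The Participation Rate equals the number of school staff who consent to participate divided by the total number of school staff who are invited". Section 9.1 hypothesises that "school staff will have high participation rates in the study", with a threshold of at least 50% consenting.

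**Who is contacted.** Under the school inclusion criteria (Section 5.1) a school must be "Willing and able to provide emails addresses for all school staff". Section 4.1 plans a census of staff at the four schools, using addresses from administrators. Section 5.5 asks for the addresses of everyone on the staff, but in one sentence limits the surveys to staff who have contact with students.

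**When eligibility is learned.** Section 5.5 says: "We will email participants a screener survey to confirm their eligibility for participation, a consent form, and a baseline survey". The Staff Screener in Section 8.1 asks for the current school (with an option for working elsewhere), age, and "How often do you interact with students at your job", with answers from daily down to never. Section 5.2 excludes staff without student contact. Section 5.4 recognises screen failures and says they will not be screened again.

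**Planning figures.** Section 9.2 starts from "The median number of teachers at each MetroWest Region high school is n=86" and four schools. For the secondary endpoints it says "We anticipate inviting at least 344 school staff to participate in the pilot study, and assuming 5% type I error rate", and concludes that "we will be able to estimate a 95% confidence interval width of no more than 0.11 for the participation rate".

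**The concern.** A staff member who receives the invitation, opens the screener and reports never having student contact cannot become a participant. Under the stated rule that person stays in the denominator and looks the same as an eligible colleague who declined. The figure set against the benchmark therefore combines two things: willingness to take part, and how broadly the school drew its email list.

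These have different consequences for the larger trial that this pilot is meant to inform (Section 2.1). Low willingness is a recruitment problem, while a broad list is a matter of how invitations are addressed. With only four schools and lists supplied by administrators, one unusually broad list could move the overall rate. The effect has one direction: leaving confirmed ineligible staff in can only lower the rate relative to consent among eligible staff.

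**Working it through.** **Inputs from the documents**
- Invited staff: 4 × 86 = 344 as a minimum (Section 9.2).
- Planned participation: 50% of 344 = 172 (Section 9.2).
- Benchmark: at least 50% (Sections 9.1 and 9.4.3).
- Stated precision: 95% interval width of at most 0.11 (Section 9.2).

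**Input assumed**
- Ineligible share f of those invited: not given, so shown from 1% to 20%.

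**Step 1: reproduce the plan's figure.** Wald width at p = 0.5 is 2 × 1.96 × √(0.25/n) = 1.96/√n. At n = 344 this is 0.106, in agreement with the stated 0.11.

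**Step 2: relate the two rates.** Let c be consent among eligible staff. Then

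stated rate = consents / invited = c × (1 − f).

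The stated rate reaches 50% only if c ≥ 50%/(1 − f).

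**Step 3: put in numbers for 344 invited.** The third and fourth columns use the smallest whole number of consents that is at least half of eligible staff. The last column is the consent among eligible staff needed to reach 172/344.

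| Assumed f | Ineligible | Consents / eligible | Consents / invited | c needed to pass |
|---|---|---|---|---|
| 1% | 3 | 171/341 = 50.1% | 171/344 = 49.7% | 172/341 = 50.4% |
| 2% | 7 | 169/337 = 50.1% | 169/344 = 49.1% | 172/337 = 51.0% |
| 5% | 17 | 164/327 = 50.2% | 164/344 = 47.7% | 172/327 = 52.6% |
| 10% | 34 | 155/310 = 50.0% | 155/344 = 45.1% | 172/310 = 55.5% |
| 20% | 69 | 138/275 = 50.2% | 138/344 = 40.1% | 172/275 = 62.5% |

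**Step 4: break-even f.** For a given c, the stated rate falls below 50% once f exceeds 1 − 0.50/c:
- c = 51%: f above 2.0% (7 or more of 344)
- c = 55%: f above 9.1% (32 or more)
- c = 60%: f above 16.7% (58 or more)

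**Step 5: precision with the smaller denominator.** 1.96/√n gives 0.108 at n = 327, 0.111 at n = 310 and 0.118 at n = 275. A width strictly within 0.11 needs n ≥ 1.96²/0.11² = 3.8416/0.0121 = 317.5. That is 318 staff, so up to 26 of 344 (7.6%) could be removed. To two decimals the stated 0.11 still holds at about f = 10%.

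**Step 6: what the screener can and cannot remove.** Only people who answer it can be classified. Take f = 10% with 155 consents. If all 34 ineligible staff answer, the revised rate is 155/310 = 50.0%. If only half of them (17, an assumption) answer, it is 155/327 = 47.4%, between the stated 45.1% and the full 50.0%.

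**The case against.** The strongest reply is that the plan is consistent as it stands. Section 9.2 applies its 50% to invited staff, the denominator in Section 9.4.3 is invited staff, and the precision figure is computed on the same base. The table in Section 3 describes these measures as showing whether the trial reached enough staff, and consented over invited is a sound measure of reach. This stands. A reader might infer that the plan contradicts itself, or that the stated rate is a biased estimate of its target. The documents support neither reading, because they never name consent among eligible staff as the target.

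It can also be said that f is probably small. Only an answer of never having student contact plainly excludes. The addresses come from the enrolled schools' own administrators, so failures on employment or age should be few. Section 4.1 explains its census by naming teaching, administrative, nursing and counselling roles, and one sentence in Section 5.5 narrows the surveys to staff with student contact. If lists are filtered before mailing, f approaches zero. This stands as a limit on size. However, no filtering step is described, and Section 5.5 relies on the emailed screener to confirm eligibility.

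A reader might further infer, because 344 is built from teacher counts, that the 50% assumption was never meant for a wider staff list. Section 9.2 does not support this: it applies 50% to school staff and uses 344 as a floor.

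Finally, the rate is reported with an interval of about ±5 points, and no stop or go rule is attached to it. That is correct, and it makes this a recommended improvement, not a serious defect.

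**Conclusion.** The point holds in a limited form. Under Section 9.4.3, staff whom the screener confirms as ineligible count as non-consent against the 50% benchmark, and nothing in the plan removes or separately reports them. The stated rate is (1 − f) times consent among eligible staff. The pass or fail result changes only if that consent lies between 50% and 50%/(1 − f): 50% to 51.0% at an assumed f of 2%, and 50% to 52.6% at 5%. The direction of the effect follows from the definition. Its size rests on f, which the documents do not give.

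The change is worth making before data are seen, because choosing a denominator afterwards, close to the threshold, would be open to question.

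**What to change.** In Section 9.4.3:
1. Define the benchmark rate as consented staff divided by invited staff minus screener-confirmed failures on the employment, age or student-contact criteria. Do not count lack of consent as a screen failure here, although Section 5.1 lists consent as an inclusion criterion; otherwise every refusal would leave the denominator.
2. Keep staff who never answer the screener in the denominator.
3. Report consented over all invited as a second figure, labelled as reach.
4. Report the number of screen failures by school.

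Also reconcile Sections 4.1, 5.1 and 5.5 on who is invited: everyone on the school's list, or only staff with student contact.

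The cost is wording, since the screener already collects what is needed. The denominator becomes slightly smaller, with an interval width of about 0.111 at 310 staff against 0.106 at 344. The eligibility of non-responders remains unknown, so the revised rate removes only part of the mixture if some ineligible staff ignore the email. The text should say so.

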#### Hypothesis: School staff will have a low attrition rate for the follow-up survey (<25% drop-out).

The Attrition Rate equals the number of school staff who failed to complete the follow-up survey divided by the total number of school staff who were consented. We will calculate an overall rate with a 95% confidence interval.

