screening/enrollment and prior to intervention delivery. We will conceal allocation from schools. This is an unblinded study. This is an educational intervention that cannot be blinded because study participants will be able to tell which condition they are in based on the content they receive. Unblinding could introduce bias, including social desirability bias, attrition bias, bias in intervention participation, and bias in reporting adverse events. Outcomes are assessed via self-reported online surveys, so there is no concern about bias about the blinding for outcome assessors.

PLANTS (Providing LGBTQ+ Adolescents with Nurturance, Trustworthiness, and Safety) intervention is an online-delivered training program, including asynchronous and synchronous activities. This intervention was informed by the Information-Motivation-Behavior theory to target skills, self-efficacy, knowledge, and outcome expectations. There are approximately 20 asynchronous online modules that cover a variety of topics including lessons on LGBTQ+ terminology, names and pronouns, resources, antibullying, gender neutral bathrooms, student confidentiality, active empathic listening, and school policies. Each module includes recorded presentations, student testimonials, activities, and downloadable resources for future reference. Every month, 7-9 lessons are opened. There are 2-3 synchronous group events delivered via Zoom that are 1.5 hours each.

The active control arm is an email-based intervention, EMAILS (E-learning to Maximize Academic Inclusion of LGBTQ+ Students), in which existing public resources for supporting, affirming, and protecting LGBTQ+ are emailed to participants. All of these resources are also provided to intervention participants. The topics of the email intervention are similar to those of PLANTS.

At the 4 enrolled schools, we will administer online surveys to all staff members (i.e., a census of teachers, administrators, nurses, counselors) via REDCap software. With staff emails provided by administrators, we will send staff a screening survey, consent form, and baseline survey. Subsequently, we will sample a subset of the intervention and control groups for individual interviews to explore implementation outcomes more deeply.

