### Additional Analyses

Participant bias assessment will compare staff participants' demographics (at baseline) to publicly available school-level data. We will report significant differences as potential validity threats.

Attrition bias assessment will compare staff respondents who completed follow-up surveys versus those who did not by baseline demographics and outcomes.

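### Attrition and participation are assessed only as rates pooled over both arms, so the low-attrition benchmark can be met despite heavy loss in the PLANTS arm, which alone supplies the primary endpoints

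*Combined protocol and SAP*

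**What the plan says.** Section 9.4.3 defines attrition as the "number of school staff who failed to complete the follow-up survey divided by the total number of school staff who were consented", and continues: "We will calculate an overall rate with a 95% confidence interval". For participation it says: "We will calculate an overall participation rate with a 95% confidence interval". The precision statements in 9.2 match this pooling, with n=344 invited for participation and n=172 consented for attrition.

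The other planned look at attrition is under Additional Analyses in 9.4.3: "Attrition bias assessment will compare staff respondents who completed follow-up surveys versus those who did not by baseline demographics and outcomes". Arm is not mentioned. Elsewhere the plan does name the arm when it wants arm-level results, as for adherence in 9.4.3 and adverse events in 9.4.4.

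Sections 4.1 and 6.3 acknowledge the threat: "Unblinding could introduce bias, including social desirability bias, attrition bias, bias in intervention participation, and bias in reporting adverse events". Section 9.3 restricts the primary endpoint population to PLANTS-arm staff with follow-up data, and 9.2 sizes the primary analysis on 75% of PLANTS participants completing follow-up (n=65).

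The benchmark itself appears in two forms. Section 9.1 says that "school staff will have a low attrition rate for the follow-up survey", with a cut of at most 25%. The heading in 9.4.3 reads "School staff will have a low attrition rate for the follow-up survey (<25% drop-out".

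**The concern.** The 75% follow-up assumption behind the primary analysis concerns the PLANTS arm, but the benchmark that would check it also counts EMAILS staff, who contribute nothing to the primary endpoints. What is asked of participants differs by arm. A full dose of PLANTS is every module plus three live events of 1.5 hours each (6.1.1, 6.1.2), while EMAILS sends links to public resources. If follow-up completion differs by arm, good retention in EMAILS can offset poor retention in PLANTS within one rate.

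Two things are at stake. First, the pilot is meant to inform a fully powered trial (2.1), whose planning needs retention by arm. Second, if dissatisfied PLANTS staff are the ones who do not respond, the primary means are biased in a way that their confidence intervals do not show.

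Participation raises a related but weaker question. Schools are randomized before staff are screened or enrolled (4.1, 6.3), so consent comes after allocation and could in principle differ by arm.

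**Working it through.** **Inputs.** Invited: 4 × 86 = 344. Consented: 0.50 × 344 = 172. PLANTS arm: 172/2 = 86. PLANTS responders: 0.75 × 86 = 64.5, stated as 65. Stated interval widths: 0.33 for the acceptability, appropriateness and feasibility scales and 10.1 for the System Usability Scale (SUS). All are from 9.2.

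**Reproducing the plan's precision.** The maximum Wald 95% width is 2 × 1.96 × √(0.25/n):
- n=344: 0.106 (stated 0.11)
- n=172: 0.149 (stated 0.15)
- n=86: 0.211 (stated 0.21)

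The plan's arithmetic is sound; the gap lies in which rates are planned.

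**What the pooled criterion permits.** Pooled attrition = (lost in PLANTS + lost in EMAILS)/172.

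| Lost in PLANTS (of 86) | Lost in EMAILS (of 86) | Pooled | At most 25% | Below 25% |
|---|---|---|---|---|
| 35 (40.7%) | 7 (8.1%) | 42/172 = 24.4% | met | met |
| 35 (40.7%) | 8 (9.3%) | 43/172 = 25.0% | met | not met |
| 42 (48.8%) | 0 | 42/172 = 24.4% | met | met |
| 43 (50.0%) | 0 | 43/172 = 25.0% | met | not met |

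In the first row, the exact 95% interval for PLANTS attrition (35/86) is 30.2% to 51.8%, wholly above the benchmark.

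**How low EMAILS attrition must be.** If PLANTS loses 40% and holds a share f of consented staff, the pooled rate reaches 25% when EMAILS attrition is (0.25 − 0.40f)/(1 − f):
- f = 0.4: 15%
- f = 0.5: 10%
- f = 0.6: 2.5%

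**How often the benchmark would then be met.** Take true PLANTS attrition of 40%, 86 per arm, and independent binomial counts. The EMAILS rates are assumptions and school clustering is ignored. The chance is the sum over a of P(A = a) × P(B ≤ 43 − a), where A and B are the numbers lost in PLANTS and EMAILS. For the strict cut, 42 replaces 43.

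| True EMAILS attrition | At most 25% | Below 25% |
|---|---|---|
| 5% | 83% | 78% |
| 10% | 54% | 47% |
| 20% | 8% | 6% |

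**Effect on the primary endpoints.** With 35 lost, 86 − 35 = 51 PLANTS responders remain. Widths scale by √(65/51) = 1.129, so 0.33 becomes 0.37 and 10.1 becomes 11.4.

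**The two cuts.** They differ only at exactly 25%. At n=172 that is 43 staff, with probability about 7% if the true rate is 25%.

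**The case against.** Several counter-arguments carry weight.

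- A reader might infer that no planned output would reveal differential loss. The documents do not support that. Baseline statistics by arm (9.4.1), within-arm summaries at each timepoint (9.4.3) and the primary table in PLANTS responders (9.4.2) would normally carry per-arm counts. Loss could be derived from them, though no such result is planned or tied to the benchmark. The PLANTS-only adherence benchmark is a partial safeguard, but it measures engagement, not survey completion.
- No document gives an expected EMAILS attrition rate, and if EMAILS loses 20% the pooled criterion would seldom be met. Incentives, reminders and contact attempts (5.5, 7.3) are described without distinction by arm. That a heavier intervention lowers survey completion is an inference.
- It is tempting to say that the planning case sits exactly on the 25% boundary. It does not. The 75% in 9.2 applies to PLANTS only, and 65/86 means 24.4% lost, which meets either cut.
- Section 3 presents the trial-implementation rates as measures of reaching enough staff. An overall rate suits that purpose, and nothing makes attrition a rule for proceeding. A PLANTS-arm rule that overrides the overall hypothesis is therefore not needed.
- On participation, allocation is concealed from schools (4.1, 6.3). The text does not settle whether staff know their arm when consenting, so differential consent is a possibility to check, not a finding.
- The difference between the two cuts may come from reading an underlined heading out of the PDF.

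The central gap remains: the plan names attrition bias as a risk and depends on PLANTS follow-up, but plans no arm-level attrition rate.

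**Conclusion.** The concern holds as a gap in the planned analysis. The pooled attrition criterion can be met at 24.4% while PLANTS loses 40.7%. This rests on 86 staff per arm and EMAILS attrition of about 10% or less, and it describes what the rule allows, not a forecast. The direct cost in precision is modest, about 13% wider intervals for the primary endpoints at 51 responders. Possible responder bias in the primary means matters more, but the documents give no basis for sizing it. The participation point is a descriptive check with no magnitude attached. The discrepancy between the two cuts is minor.

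**What to change.** In 9.4.3:

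1. Keep the overall attrition rate and add the rate in each arm with a 95% confidence interval, plus the between-arm difference.
2. Set PLANTS-arm attrition against the 25% benchmark alongside the overall rate.
3. Make the comparison of follow-up completers with non-completers by arm.
4. Report participation by arm and by school, as description, next to the overall rate.
5. After checking the source PDF, state one attrition cut in both 9.1 and 9.4.3.

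The cost is some SAP wording and a few table rows, with no new data. The downside is wider arm-level intervals: 2 × 1.96 × √(0.25 × 0.75/86) = 0.18 at 25% attrition, before any allowance for clustering by school. The PLANTS-arm comparison is also harder to meet than the pooled one.
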